3.4.5 Sample Size

All patients in the LRx database who have been prescribed Byetta in Canada during an analysis period and met the inclusion criteria will be included in the study. In similar studies in this market ~500,000 patient records have passed selection criteria for inclusion to a study sample. However the anticipated use of Byetta amongst this patient population in the first year of marketing in Canada is unknown at the present time and is projected to be modest. Upon initiation of the study, IMS Brogan will analyze the dataset to identify the number of patients available for study (the number of patients on Byetta in the analysis period). The number of Byetta patients is expected to rise in each year analyzed.

To allow for sufficient patients for a robust analysis, we will perform the first study 2 years after Byetta's launch in Canada, analyzing the two years separately (see figure 2). The analysis will be repeated in the subsequent year, to capture additional Byetta patients and identify shifts in Byetta usage.

3.4.6 Analysis Plan

The data extracted will be analyzed to complete the following 3 tables requested for each study year. The results will be provided as percent of patients who are "inferred on-label" and patients who are "inferred off-label", stratified by gender. Any off-label use in the pediatric population will be described (by gender and concomitant use). Results for the first report (year 1 and year 2 data) will be available in Q4 of 2013 and results for year 3 data will be available in Q4 of 2014.

Table 6: Indications for patients prescribed Byetta**(Patients over the age of 18)**

Indication	Male		Female	
	# of Patients	% of Patients	# of Patients	% of Patients
Inferred On-Label				
Off-Label Insulin Use				
Off-Label OAD Use				
Off-Label				

Table 7: Byetta Concomitant medications

Concomitant medications	All Patients (>17 yrs) N (%)	Inferred On-Label N (%)	Inferred off-label (all combinations) N (%)	Off-Label Insulin Use N (%)	Off-Label OAD Use N (%)	Off-Label N (%)
Oral anti-glycaemics						
Metformin						
SU						
TZD						
Others						
Insulin						

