3.1 Rationale

Exenatide is an injectable glucagon-like peptide 1 (GLP-1) receptor agonist approved as an adjunct to diet and exercise to improve glycemic control in adults with type 2 diabetes mellitus (T2DM) by the United States and Europe. Byetta (exenatide twice daily) is administered as a subcutaneous injection within 1 hour before the two main meals of the day, approximately 6 hours or more apart. Treatment is typically initiated at 5 mcg per dose, twice daily, and may be increased to 10 mcg twice daily based on the patient’s clinical response.

During Health Canada’s review of the marketing authorisation application of exenatide, Lilly provided a commitment to monitor the off-label use and compliance to the Summary of Product Characteristics (SPC) of exenatide prescriptions through a post-launch utilization study. Specifically, Health Canada requested that:

The RMP should be revised to include a post-marketing study conducted on exenatide use and adherence to labeling recommendations in Canada, similar to the drug utilization study requested by the EU Regulatory authority that is currently ongoing in various EU countries. Since preliminary information has already indicated off label use of exenatide with either TZD or insulin in the EU, the need for further study and/or additional risk management actions with these products should be specifically addressed.

Table 1: Canadian Byetta Indication

Byetta Monograph
Indication and Clinical Use:
BYETTA is indicated in combination with metformin and/or sulfonylurea to improve glycemic control in patients with type 2 diabetes mellitus, when maximally tolerated doses of these oral therapies in addition to diet and exercise do not provide adequate glycemic control.
BYETTA is indicated in combination with insulin glargine (with or without metformin) to improve glycemic control in patients with type 2 diabetes mellitus when insulin glargine (with or without metformin) in addition to diet and exercise, does not provide adequate glycemic control
Contraindication:
BYETTA should not be used in the pediatric patient population.

BYETTA should not be used in patients with end-stage renal disease or severe renal impairment (creatinine clearance <30 mL/min), including patients receiving dialysis

BYETTA is contraindicated in patients with diabetic ketoacidosis, diabetic coma/precoma or type 1 diabetes mellitus.

Source: Byetta Drug Product Monograph, Canadian Pharmacists Association, online version, April 2011.

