3.2.1 Primary Objectives

To evaluate exenatide use outside labeling indications in Canada.

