3.4.2 Study Design

This will be a retrospective database study using IMS Brogan's LRx dataset, in which de-identified patient level prescription information will be used to evaluate adherence to the labeling recommendations for exenatide use in Canada. The study will be based on a 'Look-Back,' 'Analysis' and 'Follow-Up' period as shown in figure 1. Patients will be selected for the study if they are receiving a Byetta prescription in the 12 month analysis period.

[figure not shown]
The 'Look-back' period is used to ensure that each patient within the analysis period has at least 6 months of data prior to first Byetta script. This eligibility period ensures that a patient whose first Byetta script occurs at the start of the analysis period can be classified appropriately and that they are present in the database prior to the first script. Similarly, the 'Follow-up' period is used to ensure that each patient has at least 3 months of data following the last script within the analysis period. This ensures that the duration of therapy for a patient who receives their last script at the end of the analysis period is accounted for and can have their therapy appropriately classified, specifically around the concomitant use of Byetta with insulin or TZDs.

Figure 1: Study periods proposed for analysis of Byetta use in the 1st year post launch

In addition to the study period proposed in figure 1, the analysis will be conducted for Year 1, 2 and 3 post Byetta launch allowing for an analysis of trends in Byetta use over time, as shown in figure 2. Study 1* will provide results on Year 1 and 2 and would commence at the availability of Aug 2013 data. Study 2** will provide Year 3 results and would commence at the availability of Aug 2014 data.

Figure 2: Three proposed analysis periods for study post Byetta Launch

Note: Implies that the look-back period and the follow-up period are at least 6 months and 3 months for each patient, respectively.

Note: Month 1 = Date of First Byetta Sale = June 2011

*Study 1: All Byetta prescriptions in the database in months 0-24, post launch

** Study 2: All Byetta prescriptions in the database in months 25-36, post launch

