3.4.4 Study Outcomes and Definitions

[figure not shown]
The primary outcome of interest is the off label use of Byetta in Canada.

A patient's therapy type will be inferred by identifying if a patient switches between, or adds on to therapies, as shown in figure 3.

Mono Therapy is defined as a patient receiving a specific therapy (Therapy 1) prior to a different therapy (Therapy 2) where Therapy 1 is not detected after Therapy 2 initiation. Mono therapy for this study, refers to a patient received a prescription for only one product at a given time.

Concomitant Therapy is defined as a patient receiving a specific therapy (Therapy 1) prior to a different therapy (Therapy 2) where Therapy 1 is detected after Therapy 2 initiation.

Figure 3: Distinguishing between add-on and switch therapies

Patients will be selected for the study if they receive a Byetta script anytime during the analysis period and if they met the inclusion criteria. To identify on-label vs. off-label use, patient history will then be used to classify patients as "inferred on-label" if they also received Metformin and/or SU or Lantus during the study (Business rules 1 and 2 in Table 5).

All other patients that do not meet the criteria for use of Byetta with metformin and/or SU or Lantus will be classified as “inferred off-label”. The group of patients classified as “inferred off-label” will then be further classified to gain a better understanding of the trends in “inferred off-label” use of Byetta (Business rules 3-10 in Table 5).

The Business rules described in Table 5 are prioritized to ensure the appropriate classification of each patient. Therefore patients will be classified based on the highest rank business rule. For example, if a patient receives scripts for both Metformin and other insulin during the analysis period, they will be classified as “inferred on-label” as they have a script for metformin and therefore are classified by business rules 1 and 2

Note: The patient classification categories (‘Inferred Adherence Label’) can be modified in the initial phase of the project.

Table 5: Business rules applied to classify patients as “on-label” vs. “off-label”

(The business rules have been structured to align with the Canada monograph for Byetta indication and clinical use (see Table 1) and will be finalized upon study initiation).

Rank	Business Rules	Cohort Description	Inferred Adherence Label

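### One best-ranked label per patient per study year hides off-label Byetta use in patients with any metformin, sulfonylurea or Lantus evidence, and the limitations section states only the opposite bias

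*Protocol*

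**What the plan says.** Protocol 3.4.4 puts each patient through the ten ranked rules of Table 5 and keeps one: "Therefore patients will be classified based on the highest rank business rule". Rank 1 is continued use of Byetta with metformin and/or a sulfonylurea, or with Lantus. Rank 2 is evidence of both without their being prescribed together. Both are inferred on-label. Levemir, human basal insulin, TZD, Byetta alone and other insulin come lower. The protocol gives its own example of the override: "if a patient receives scripts for both Metformin and other insulin during the analysis period, they will be classified as" inferred on-label.

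Protocol 3.4.6 fixes the unit of the result ("The results will be provided as percent of patients who are" on-label or off-label). It lays out Table 6 (patients by label and sex) and Table 7 (concomitant drugs by label group), completed for each study year. It announces three tables. Two are visible, so nothing is said here about a third.

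On purpose, 3.1 describes a "commitment to monitor the off-label use and compliance to the Summary of Product Characteristics (SPC) of exenatide prescriptions". The regulator's request in the same section is for a "post-marketing study conducted on exenatide use and adherence to labeling recommendations in Canada", and the primary objective in 3.2.1 reads "To evaluate exenatide use outside labeling indications in Canada". On bias, 3.4.7 says only that off-label use is probably over-estimated, because the on-label rules are strict.

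**The concern.** A patient's Byetta treatment can change within a study year, and the label keeps only the most favourable evidence. Table 6 therefore answers whether a patient had metformin, a sulfonylurea or Lantus at any time in the window. It does not answer how much Byetta use was outside the label.

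This affects the primary outcome of a study done to meet a regulatory commitment. A reader who relies on 3.4.7 would treat the off-label percentage as an upper estimate, although the ranking pushes it down.

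Trends are also exposed. Section 3.4.7 acknowledges that the amount of data differs between patients. Under a rule that looks for evidence at any time, more data can move a patient from off-label to on-label but never back. If observed time per patient differs between Years 1, 2 and 3, part of any apparent shift could come from the rule.

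**Working it through.** The protocol gives no figure to reproduce: no expected off-label share, sample size or precision. The check traces the rules and then illustrates the size.

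**Tracing Table 5**

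- Patient A takes metformin with the first Byetta scripts, then Byetta alone. Rank 1 or 2 applies and Table 6 shows on-label. Rank 6 (Byetta alone) is never reached, because it requires that nothing else was prescribed in the analysis period. Neither table shown reveals the Byetta-alone spell.
- Patient B takes metformin at some point and a TZD or other insulin at some point. Table 6 shows on-label. The patient is counted in the TZD or Insulin row of the on-label column of Table 7, with no indication of when.
- Patient C takes metformin only in the look-back, then Byetta alone. The Table 5 footnote lets evidence come from the look-back or look-forward periods, so rank 2 makes this patient on-label. The rank 2 cohort description places both drugs in the analysis period and would not. The two texts need reconciling.

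**Direction**

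To be labelled off-label, a patient must have no qualifying metformin, sulfonylurea or Lantus evidence, so on the recorded data none of that patient's Byetta scripts was on-label by these rules. A patient labelled on-label may have any mixture. Within a patient, the single label can therefore hide off-label scripts but cannot create them. The direction comes from the rank order together with the patient unit: with the ranks reversed, a mixed user would count as off-label and the bias would run upward.

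**Size (assumed inputs only)**

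One patient with 12 Byetta scripts and metformin alongside the first 2 has 10/12 = 83% of scripts outside the combination and contributes 0% to Table 6.

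Let f be the share of all patients who are labelled on-label but have some off-label scripts, and s the off-label share of their scripts. With equal scripts per patient, the missed share of scripts is f × s:

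- f = 5%, s = 2/12: 0.05 × 0.167 = 0.8 points
- f = 10%, s = 6/12: 0.10 × 0.50 = 5.0 points
- f = 20%, s = 10/12: 0.20 × 0.833 = 16.7 points

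A second set of assumptions writes the script-level share as p + (1 − p) × q × r. Here p is the share of patients labelled off-label, q the share of the remaining patients who are mixed, and r the off-label share of their scripts. For p = 10%, q = 10%, r = 50%, this is 0.10 + 0.90 × 0.10 × 0.50 = 14.5%, against 10% reported. Over p = 5 to 20%, q = 5 to 30% and r = 25 to 75%, the gap runs from 0.80 × 0.05 × 0.25 = 1.0 point to 0.95 × 0.30 × 0.75 = 21.4 points.

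**Unequal scripts per patient**

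Suppose 10 of 100 patients are off-label with 2 scripts each and 90 are on-label with 12 each. Total scripts are 20 + 1,080 = 1,100. If 10 of the 90 are mixed with half their scripts off-label, off-label scripts are 20 + 10 × 6 = 80, and 80/1,100 = 7.3%. That is below the patient figure of 10%, although 60 off-label scripts are hidden. A script share need not exceed the patient share.

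**The case against.** Several stronger readings are tempting and the protocol does not support them.

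- A reader might infer that the single label is the only result. Table 7 does give TZD and insulin counts within the on-label group, which also serves the secondary objective. What stands is that those counts carry no timing and that Byetta-alone spells are missing from both tables shown.
- A reader might infer that the patient unit contradicts the commitment. Only the narrative in 3.1 attaches compliance to prescriptions. The request and the objective speak of use and fix no denominator. The line in 3.4.2, "All Byetta prescriptions in the database in months 0-24, post launch", defines which data enter Study 1, and the same section selects patients. This is a mismatch, not a contradiction.
- A reader might infer that the planned percentage must lie below the script-level one. The 7.3% example shows otherwise.
- A reader might infer that LRx holds every script, so that script-level compliance can simply be read off. Section 3.3 puts coverage at 74.6% of volume, and Table 3 accepts that patients sometimes use other pharmacies. A missing metformin fill does not prove that metformin was stopped.

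It is also fair that 3.4.4 leaves the categories open to modification at the start and that 3.4.7 calls the result an estimate. Neither tells the reader that the ranking lowers off-label use. The openness to modification makes the change easy and does not make it unnecessary.

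**Conclusion.** The concern holds in a limited form. One best-ranked label per patient per study year treats all Byetta use of a mixed user as on-label in Table 6, whether the off-label spell came earlier or later. Within a patient this works in one direction only, and 3.4.7 names only the opposite one.

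The protocol does not show that off-label use will be under-estimated overall. Fills missed through incomplete coverage push the other way, and the net direction is unknown. The size is also unknown: 0.8 to 16.7 points rests on assumed shares of mixed users and on equal scripts per patient. The plan should change, because the result is the primary outcome and the extra split can be built from the same extract.

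**What to change.** - Keep the ranked Table 6. Add, by study year and sex, a split of patients into all Byetta use on-label, some off-label use, and all off-label. Judge each Byetta script by the tracked drugs being taken on that date, under an overlap or grace-period rule stated in advance. The rule should also say how a script is classed when an on-label and an off-label partner drug are taken together.
- Report the off-label share of Byetta scripts as a supportive result, with confidence intervals clustered on patient. It should not replace the headline, because it depends more heavily on the overlap rule and on complete capture of fills.
- Amend 3.4.7 to say that the best-rank rule biases off-label use downward, alongside the sources of over-estimation.
- Reconcile the rank 2 cohort description with the Table 5 footnote on the window for evidence.

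The cost is extra programming on the same script-level data and an assumption about how long each fill lasts. That assumption may count refill gaps, or fills at other pharmacies, as off-label, since LRx covers about 75% of volume. Vary the grace period as a sensitivity analysis and show the range.

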3.4.3 Study Population

Inclusion/Exclusion Criteria:

All patients in the LRx database who have been prescribed Byetta in Canada during the analysis period will be included in the study. Patients with inconsistent records and/or insufficient data, as shown in table 3, will be omitted to restrict the analysis to a consistent and robust patient sample.

Exclusion criteria are required since the pharmacy data (LRx) is driven through data entry at the individual stores. The criteria are used to filter out transactions that either have entry mistakes or have place-holder information that is not accurate. The exclusion criteria are established to ensure a consistent record for patients in the study sample. Inclusion and exclusion criteria may be modified during the initial stages of the project.

Table 3: Exclusion criteria applied to remove patients with inconsistent Rx history

Criteria	Conditions for Exclusion	Rationale
Demographic Criteria	Patients without a consistent year of birth, province, or gender	Patients without a consistent demographic record of gender, year of birth and province are not reliable due to inconsistencies
Constant Store Criteria	Patients at stores with inconsistent reporting after May 2011	Stores with inconsistent recorded information will not have accurate information on what prescriptions a patient received
Max Rx Criteria	Patients with more than 208 Rx/year	This is to eliminate pharmacist error
Min Rx Criteria	Patients with fewer than 6 Rx	Patient with less than 6 prescriptions are excluded because there is the potential for including the same patient multiple times as occasionally patients fill prescriptions at different pharmacies when traveling or for convenience
Consistent Patients	Remove patients without any prior Rx at a store	Removing patients without any other prior prescriptions at a store also eliminates patients who have changed pharmacies and may be included multiple times in the data
Analysis Period	Remove patients without any	Patients who do not have a prescription

	Rx in the Analysis Period	in the analysis period cannot be included as they do not have any prescriptions to analyze
12 Month Gap	Remove patients with a year gap between Diabetes Rx	Patients with a year gap between diabetes prescriptions are likely to have filled prescriptions at an alternative pharmacy and could be counted multiple times in the data set

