6-month look back data	Remove patients without 6 months of data prior to first Byetta script	Ensures all patients are present in the dataset and have a consistent record for analysis
3-month Follow-up data	Remove all patients without 3 month follow-up data	Ensures patients therapy can be appropriately classified as add-on or switch

To identify other diabetes therapies for the selected patients, prescriptions for product groups in table 2 will also be tracked for selected patients

Table 4: Diabetes therapies tracked for Byetta patients

Category	Product Group	Product
Insulin	Premix Human	Lilly Human Premix, NNCI Human Premix
	Premix Analog	Humalog Mix, NovoMix
	Basal Human	Novolin NPH, Humulin N
	Basal Analog	Lantus, Levemir
	Rapid Human	Humulin R, Novolin Toronto
	Rapid Analog	Apidra, Humalog, NovoRapid
OAD	Metformin	Metformin
	Sulfonylurea (SU)	Diamicon / Diamicon MR, Gliclazide, Glimepiride/ Amaryl, Glyburide
	Thiazolidinedione (TZD)	Avandamet, Avandaryl, Actos, Avandia, Generic Pioglitazone
	PPG Regulators	GlucNorm, Starliz, Generic Repaglinide
	DPP4	Januvia, Onglyza, Janumet, Trajenta

	Prandase	Prandase
GLP1	GLP1	Victoza, Byetta

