1	Concomitant use of* Byetta with metformin (met) and/or sulfonylurea (SU), OR Concomitant use of Byetta with Lantus	Met and/or SU or Lantus is prescribed with Byetta	Inferred On-label
2	Evidence of** Byetta and metformin and/or sulfonylurea OR Evidence of Byetta and Lantus	Met and/or SU or Lantus is not prescribed with Byetta, but both appear in the analysis period	Inferred On-label
3	Evidence of Byetta and Levemir	Levemir is prescribed in the analysis period	Off-Label Insulin Use
4	Evidence of Byetta and Human Basal Insulin	Human basal insulin is prescribed in the analysis period	
5	Evidence of Byetta and thiazolidinedione (TZD)	TZD is prescribed in the analysis period	Off-Label OAD Use

6	Byetta Alone	No other products prescribed in the analysis period	Inferred Off-label
7	Evidence of Byetta and all other insulin	Other insulin is prescribed in the analysis period	
8	Evidence of Byetta and all other OADs	Other OADs are prescribed in the analysis period	
9	Pediatric Patients	Patient is under the age of 18 (<18)	
10	All other combinations	All other combinations	

Note: Evidence of Diabetic ketoacidosis, diabetic coma/precoma and end stage renal disease cannot be inferred from the dataset; therefore we will not be able to identify these patients as a separate group

* "Concomitant use of..." refers to continued use of Byetta and other product

** "Evidence of..." refers to anytime within the study period including look-back or look forward periods

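### History filters can remove some paediatric Byetta users before they are counted; separately, Table 6's age label drops 18-year-old adults

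*Protocol*

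**What the plan says.** Table 1 in section 3.1 of the Protocol lists paediatric use under contraindications: "BYETTA should not be used in the pediatric patient population". Section 3.4.6 undertakes to report such use: "Any off-label use in the pediatric population will be described (by gender and concomitant use".

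Section 3.4.5 limits the study to patients who pass the selection criteria. Table 3 in section 3.4.3 sets those criteria for all Byetta patients. Five of them concern the length or completeness of the prescription record:

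- minimum prescriptions: "Patients with fewer than 6 Rx" are excluded;
- an earlier prescription at the same store is required;
- a year-long gap between diabetes prescriptions excludes the patient;
- look-back: "Remove patients without 6 months of data prior to first Byetta script";
- 3 months of follow-up data are required.

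A further criterion checks demographic consistency and excludes "Patients without a consistent year of birth, province, or gender". No criterion has an exception for minors.

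Age appears in three places. Table 5, rank 9 (section 3.4.4) defines the paediatric group: "Patient is under the age of 18 (<18". Table 6 (section 3.4.6) is headed "Patients over the age of 18". The total column of Table 7 (same section) is headed "All Patients (>17 yrs".

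**The concern.** There are two separate points.

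**Filters before the count.** Of the contraindications in Table 1, paediatric use is one that this database can show. Section 3.4.7 concedes that ketoacidosis, coma or precoma and end-stage renal failure cannot be inferred. Identifying a paediatric user takes one Byetta script and an age. If the history filters run first, a low or zero paediatric count may partly reflect the filters, and a reader of the report could not tell. Section 3.4.7 warns only that off-label use is probably overstated; a paediatric user lost to a filter is an error in the other direction.

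**Conflicting age labels.** Tables 6 and 7 report the same label categories but, as headed, for different populations. Their totals would not agree, and one year of adult age would be missing from the main on-label/off-label table.

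**Working it through.** The Protocol gives no paediatric count, rate or sample-size figure, so there is no stated figure to reproduce. The check compares the rules with one another.

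**1. What each output needs, against what Table 3 requires**

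| Table 3 criterion | Needed to count users under 18? | Needed to describe concomitant use? |
|---|---|---|
| Consistent year of birth | Yes, to assign age | Yes |
| At least 6 prescriptions | No | Not strictly; guards against duplicates |
| Earlier prescription at the store | No | Helps; guards against duplicates |
| No year-long gap in diabetes prescriptions | No | Guards against duplicates |
| 6-month look-back | No | Yes, in part |
| 3-month follow-up | No | Yes, to separate add-on from switch |

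The minimum-prescription rule is not restricted to Byetta. Two illustrative minors, each with one Byetta script:

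- five other prescriptions: 1 + 5 = 6, so the patient passes this rule;
- four other prescriptions: 1 + 4 = 5 < 6, so the patient is removed.

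What decides the matter is how thin the whole record is, not how short the Byetta exposure is.

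**2. Age labels side by side**

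| Age | Paediatric, Table 5 (<18) | Table 6 as headed (>18) | Table 7 as headed (>17) |
|---|---|---|---|
| 16 | yes | no | no |
| 17 | yes | no | no |
| 18 | no | **no** | yes |
| 19 | no | yes | yes |

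Only age 18 is placed inconsistently. If N6 is the Table 6 total over both sexes and N7 the Table 7 total, then N7 − N6 = the number of 18-year-olds. Reading Table 6 as 18 and over makes the difference 0 and puts every age in exactly one group.

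**3. If only year of birth is held (an assumption)**

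Let d = script year − birth year.

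- d ≤ 17: certainly under 18.
- d = 18: aged 17 or 18. Example: born 1994, script in June 2012, 2012 − 1994 = 18.
- d ≥ 19: certainly 18 or older.

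Assume births are spread evenly over the year, and let f be the fraction of the year elapsed at the script. The share of the d = 18 group still aged 17 is 1 − f: 100% on 1 January, 1 − 5/12 = 58% on 1 June, 50% on 1 July and 0% on 31 December. With scripts also spread evenly, the average is 50%. For any script year this concerns one birth-year cohort only.

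**The case against.** The filters have stated purposes. Section 3.4.3 says they remove entry mistakes and placeholder values, and several are meant to stop one person being counted more than once after using different pharmacies. In a very small count, a duplicate or a false birth year weighs heavily. The promised description by concomitant use does need prescriptions before and after Byetta initiation. Since section 3.4.5 confines the study to patients who pass the criteria, *any* paediatric use can fairly be read as any use within that sample. Section 3.4.3 also allows the criteria to be modified early in the project.

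Most of this stands, and it rules out replacing the filtered figure with an unfiltered one. It does not rule out showing both. The option to modify criteria does not commit the study to a paediatric count, and section 3.4.7 does not disclose the possible loss.

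A reader might infer more than the Protocol supports:

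- *That a child given one or two Byetta scripts is necessarily deleted.* The 6-prescription rule covers all prescriptions, and the look-back and follow-up rules ask for data, not Byetta data. Such a child may be removed but need not be.
- *That the Table 6 label hides contraindicated use.* Under Table 5 an 18-year-old is an adult, so the gap drops adults from an adult table. Tables 5 and 7 agree with each other, so Table 6 is most likely a loose wording of 18 and over.
- *That the under-18 cut cannot be applied exactly.* Year of birth is the only age field named, but the Protocol does not say that a full birth date is unavailable. Deriving age is also commonly left to the SAP, so its absence here is no fault.

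**Conclusion.** Both points hold, and both are minor in size.

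1. **Paediatric count: a cheap improvement, not an error.** Table 3 can remove some paediatric users whose database record is thin, before section 3.4.6 describes them, and section 3.4.7 is silent on it. The number affected cannot be derived from the Protocol. I expect it to be small, but the result is itself a count, so each lost case shows.
2. **Table 6 heading: wrong as written.** It conflicts with Tables 5 and 7. Taken literally, 18-year-old adults are in Table 7 but in neither Table 6 nor the paediatric description, and the denominators differ by their number. No paediatric use is missed through this.

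The first point assumes that Table 3 is applied to minors as to everyone else, which is how sections 3.4.3 and 3.4.5 read. The year-of-birth ambiguity arises only if the full birth date is not held. The 50% average applies only to the ambiguous cohort and rests on an even spread of births and scripts.

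**What to change.** - **Section 3.4.6:** report, for each study year, the number of Byetta patients under 18 before the five history filters (keeping the consistent year-of-birth check) beside the number after them. Restrict the description by concomitant use to the filtered patients.
- Label the pre-filter figure an upper count for the database, because it may include duplicate patients and birth-year entry errors.
- **Section 3.4.7:** add a sentence that the Table 3 filters may remove some paediatric users with little recorded history.
- **Tables 6 and 7:** define adults as 18 and over in both, matching the under-18 rule in Table 5, and check that the two totals agree.
- **Only if year of birth alone is held:** show patients whose script year minus birth year equals 18 separately, as of uncertain age, and treat them the same way in both tables.

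The cost is one extra count on data already extracted (section 3.4.5 already plans an initial count of Byetta patients), one limitation sentence and one corrected heading. The downside is that the pre-filter count is less clean than the filtered one, hence its label and its place beside that figure.
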